8.14.2. Non-Serious Adverse Event Reporting Requirements

All AEs will be reported on the AE page(s) of the CRF. It should be noted that the form for collection of SAE information is not the same as the AE CRF. Where the same data are collected, the forms must be completed in a consistent manner. For example, the same AE term should be used on both forms. AEs should be reported using concise medical terminology on the CRFs as well as on the form for collection of SAE information.

8.14.3. Sponsor Reporting Requirements to Regulatory Authorities

Adverse event reporting, including suspected unexpected serious adverse reactions, will be carried out in accordance with applicable local regulations.

9. DATA ANALYSIS/STATISTICAL METHODS

9.1. Sample Size Determination

The study will be powered to show non-inferiority of pregabalin with respect to placebo on the mean deviation score from the Humphrey threshold test, a secondary endpoint. Non-inferiority from placebo will be declared with respect to mean deviation if the lower bound of the 95% 2-sided confidence interval of the difference in mean deviation scores between pregabalin and placebo is greater than -2.0 decibels (dB). Assuming the mean deviation scores to be equal and assuming estimated common standard deviation of 1.3 dB, then the proposed sample size of 187 subjects will provide greater than 85% power to show non-inferiority of pregabalin to placebo.

The estimated common standard deviation of 1.3 dB, from the 15 March 2019 dataset prepared for the annual Internal Review Committee (IRC) blinded review (refer to [Section 9.6](#)), was used to re-estimate the sample size for the secondary endpoints. Previously, at the time of study design, a common standard deviation of 5.6 dB had been used for the sample size determination based on literature.¹² Table 1 below used common standard deviation (1.3) and the number of enrolled subjects (n=187) to estimate the study power.

Table 1. Study 1096 Sample Size and Power for the Secondary Endpoint

Total Number of enrolled subjects	Common Standard Deviation	Non-inferiority Margin	Power
187	1.3	-2.0	>99.9%

For the primary endpoint, the proposed sample size will provide >99.9% power to show non-inferiority of pregabalin to placebo with respect to the proportion of subjects with a repeated decrease in the same 5 visual field points, with non-inferiority declared if the upper bound of the 95% confidence interval for the difference between pregabalin and placebo does not exceed 10% and assuming a proportion of subjects meeting primary endpoint definition of 1% for both groups. Table 2 below provided the estimated power for the primary endpoint.

Table 2. Study 1096 Sample Size and Power for the Primary Endpoint

Total Number of enrolled subjects	Proportion of Subjects Meeting Primary Endpoint Definition	Non-inferiority Margin	Power
187	1%	10%	>99.9%

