2.3. Statistical Power and Sample Size Considerations

The study will be powered to show non-inferiority of pregabalin with respect to placebo on the mean deviation score from the Humphrey threshold test, a secondary endpoint.

Non-inferiority from placebo will be declared with respect to mean deviation if the lower bound of the 95% 2-sided confidence interval of the difference in mean deviation scores between pregabalin and placebo is greater than -2.0 decibels (dB). Assuming the mean deviation scores to be equal and assuming estimated common standard deviation of 1.3 dB, then the proposed sample size of 187 subjects will provide greater than 85% power to show non-inferiority of pregabalin to placebo.

The estimated common standard deviation of 1.3 dB, from the 15 March 2019 dataset prepared for the annual Internal Review Committee (IRC) blinded review (refer to Section 9.6), was used to re-estimate the sample size for the secondary endpoints. Previously, at the time of study design, a common standard deviation of 5.6 dB had been used for the sample size determination based on literature.² Table 1 below used common standard deviation (1.3) and the number of enrolled subjects (n=187) to estimate the study power.

Table 1. Study 1096 Sample Size and Power for the Secondary Endpoint

Total Number of enrolled subject	Common Standard Deviation	Non-inferiority Margin	Power
187	1.3	-2.0	>99.9%

For the primary endpoint, the proposed sample size will provide >99.9% power to show non-inferiority of pregabalin to placebo with respect to the proportion of subjects with a repeated decrease in the same 5 visual field points, with non-inferiority declared if the upper bound of the 95% confidence interval for the difference between pregabalin and placebo does not exceed 10% and assuming a proportion of subjects meeting primary endpoint definition of 1% for both groups. Table 2 below provided the estimated power for the primary endpoint.

Table 2. Study 1096 Sample Size and Power for the Primary Endpoint

Total Number of enrolled subjects	Proportion of Subjects Meeting Primary Endpoint Definition	Non-inferiority Margin	Power
187	1%	10%	>99.9%

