8. STATISTICAL METHODOLOGY AND STATISTICAL ANALYSES

8.1. Statistical METHODS

The primary analysis will compare the difference in proportions for the primary endpoint (based on a 2x2 contingency table combined across centers) using a 2-sided 95% confidence interval. Because it is expected that the proportions will be small for each treatment group, unconditional exact methods (StatXact or Proc-StatXact)² will be used to compute the confidence interval. Or the following code may be used.

```

/***
*** Hypothetic Example of calculated Exact approximation 95% CI
*** where there are 4 cases of deterioration and all 4 belong to PGB
***/

%macro pairs(x1px2=,nper=);
%do x1=0 %to &x1px2;
  data a;
  x2=&x1px2 -&x1;
  r=0; d=1; w=&nper-&x1; output;
  r=1; d=1; w=&x1; output;
  r=0; d=2; w=&nper - x2; output;
  r=1; d=2; w=x2; output;
run;
proc freq data=a;
```

```
tables d*r / norow nocol nopct exact riskdiff(cl=newcombe);  
exact riskdiff(method=score);  
weight w;  
output out=diffs riskdiff;  
  
run;  
  
data diffs2; set diffs;  
  
keep x1 n1 x2 n2 _rdif2 _x1_rdif2 xu_rdif2;  
x1=&x1; n1=&nper; x2=(&x1px2 - &x1); n2=&nper;  
  
run;  
  
proc append base=pairvary data=diffs2; run;  
  
%end;  
  
%mend pairs;  
  
*****;  
  
%pairs(x1px2=4,nper=142); * where there are 4 cases of deterioration  
and all 4 belong to PGB  
  
run;
```

Continuous measures (MD, visual acuity) will be analyzed using an ANCOVA main effects model, with treatment and study center in the model and the respective baseline score as a covariate. Output from the ANCOVA models will include adjusted (least squares) means and standard errors for each treatment group, p-values for the pregabalin versus placebo comparison, and 95% confidence intervals on the difference in LS means between pregabalin and placebo.

The only time point analyzed is Week 12 (or last observation, for patients who terminate early). Ophthalmologic data collected at Week 6 and follow-up will be summarized descriptively but not analyzed inferentially, unless it is used as the termination time point in the primary analysis

Centers with fewer than 4 patients will be combined with other centers prior to breaking the blind. Centers with 4 or more patients may be combined with other centers as needed, or may be left as separate centers. The pooling will be done geographically if possible. These pooled centers will be used in place of center in the analyses that include center in the model.

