8.2. Statistical Analyses

8.2.1. Primary Analysis

The primary endpoint will be analyzed using a non-inferiority analysis. The difference in proportions between pregabalin and placebo in the per protocol population will be compared using a 2-sided 95% confidence interval (CI). Non-inferiority will be demonstrated if the upper CI bound is less than 0.10 (10%).

The primary analysis is based on the Per Protocol set and the primary endpoint proportion of patients with visual field deterioration. A 2-sided 95% confidence interval on the difference in proportions between pregabalin and placebo will be constructed using unconditional exact methods. To support interpretation of the primary analysis, an analysis as described above but based on the ITT population rather than the Per Protocol set, will be performed. In this analysis, patients with a decrease in ≥ 5 points at termination but no repeat visit will be treated as if they did have a repeat visit that confirmed the decrease.

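### The stated >99.9% power for the primary endpoint does not hold for the planned unconditional exact interval (about 99.3% with the score statistic), and the SAP text does not name the statistic that this interval depends on

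*Protocol*

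**What the plan says.** **Primary power.** Protocol 9.1 states that "the proposed sample size will provide >99.9% power to show non-inferiority of pregabalin to placebo with respect to the proportion"; the proportion meant is the primary endpoint, deterioration in five or more points that a second test confirms. SAP 2.3 says the same: "For the primary endpoint, the proposed sample size will provide >99.9% power to show" non-inferiority. Table 2 in each document gives the inputs: 187 subjects, 1% in each group, 10% margin. Neither says how the power was computed. The protocol Summary gives >90% for the same endpoint and rate.

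**Planned analysis.** SAP 8.1 explains its choice of interval: "Because it is expected that the proportions will be small for each treatment group, unconditional exact methods" will be used, through StatXact or, alternatively, SAS code that may be used. SAP 8.2.1 confirms it: "A 2-sided 95% confidence interval on the difference in proportions between pregabalin and placebo will be constructed using unconditional exact methods". The only exact statistic named anywhere is in that optional code, "exact riskdiff(method=score"; the same code also requests a Newcombe interval. The primary set is Per Protocol. Protocol 9.4.1 and SAP 5.2 expect it to be close in size to the number randomised, without giving a loss rate.

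**Mean deviation.** With an SD of 1.3 dB and a margin of -2.0 dB, the Protocol 9.1 text says that "the proposed sample size of 187 subjects will provide greater than 85% power to show non-inferiority of pregabalin to placebo". Its next paragraph says that "Table 1 below used common standard deviation (1.3) and the number of enrolled subjects (n=187) to estimate the study power", and that table shows >99.9%. SAP 2.3 has the same pair.

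**The concern.** SAP 8.1 turns to exact methods because events are expected to be rare. Rare events are also where a normal approximation to power is least reliable. A power statement given to a tenth of a percent, accompanying a reduction to about 187 subjects, should hold for the interval that will decide the trial.

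The term unconditional exact also does not define one interval. The result depends on the statistic used to order the possible tables. If the SAP text leaves that open, the power and the confidence bound are both open.

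The mean-deviation sentence raises a smaller question, because one set of inputs carries two power figures.

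**Working it through.** **Inputs.** 1:1 allocation with about 93 per arm (Protocol 3); 1% event rate in both arms and a margin of 0.10 (Protocol 9.1, Table 2); two-sided 95% interval, hence one-sided 0.025 (SAP 4.2); unconditional exact method (SAP 8.1, 8.2.1); score statistic (SAP 8.1 code only).

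**Step 1: reproduce the stated figure.** Normal approximation with unpooled variance:

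Φ(0.10 / √(2 × 0.01 × 0.99 / 93) − 1.96) = Φ(6.853 − 1.960) = Φ(4.893) = 0.9999995.

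Enumerating all outcomes under a Wald interval gives 99.97%. Both agree with >99.9%.

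**Step 2: power of the planned interval with the score statistic.** All pairs of event counts were enumerated and ordered by the Farrington-Manning score statistic at a difference of 0.10. The p-value was maximised over the nuisance rate and compared with 0.025. At 93 v 93, a result passes with up to 3 pregabalin events against 0 placebo events, 4 against 1 or 2, and 5 against 3. For example, 3 v 0 gives p = 0.0151 and passes; 4 v 0 gives p = 0.0382 and fails.

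The power can be checked by hand from the binomial distribution (n = 93, rate 0.01):

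| Placebo events | Probability | Fails if pregabalin events reach | Probability | Product |
|---|---|---|---|---|
| 0 | 0.3927 | 4 | 0.01445 | 0.00567 |
| 1 | 0.3689 | 5 | 0.00251 | 0.00093 |
| 2 | 0.1714 | 5 | 0.00251 | 0.00043 |
| 3 | 0.0525 | 6 | 0.00036 | 0.00002 |

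The products sum to 0.00705; higher placebo counts add a negligible amount. Power is 1 − 0.00705 = 0.99295. The chance of failure is about 0.7%, where >99.9% implies less than 0.1%.

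**Step 3: other methods and sizes** (1% per arm).

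| Interval | Per arm | Power |
|---|---|---|
| Exact, score | 93 v 93 | 99.30% |
| Exact, score | 93 v 94 | 99.30% |
| Exact, score | 94 v 93 | 99.27% |
| Newcombe (also in the code) | 93 v 93 | 99.30% |
| Wald with continuity correction | 93 v 93 | 99.80% |
| Exact, score | 90 v 90 | 98.96% |
| Exact, score | 85 v 85 | 99.1% |
| Exact, score | 80 v 80 | 97.5% |
| Exact, score | 142 v 142 | 99.99% |

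The sizes below 93 are illustrations, since the documents give no loss rate. Power does not fall smoothly, because the permitted event counts change in whole steps.

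**Step 4: the same interval ordered by the unstandardised difference.** Power at 93 v 93 is 0.0011, about 0.1%. The p-value is maximised over all nuisance rates, and the worst case lies near the middle of the range. With rates of 0.55 and 0.45 the standard error is √(2 × 0.2475 / 93) = 0.073, so the margin is only 0.10 / 0.073 = 1.37 standard errors, short of 1.96. Under this ordering even 0 v 0 events fails; a pass needs at least 5 more placebo events than pregabalin events.

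**Step 5: mean deviation.** Power = Φ(2.0 / (SD × √(2/n)) − 1.96).

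- SD 1.3, 93 per arm: Φ(10.49 − 1.96) = Φ(8.53), essentially 100%. This supports Table 1.
- SD 5.6 (the earlier value in Protocol 9.1), 142 per arm: Φ(3.009 − 1.960) = Φ(1.049) = 85.3% (85.1% with the noncentral t).

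**The case against.** A reader might infer that >99.9% is a miscalculation. The documents do not support that. They do not say that Table 2 was computed for the exact interval, and Step 1 reproduces the figure by two ordinary methods. Approximating power and then analysing exactly is common practice, and the gap is only 0.6 to 0.7 percentage points. What stands against the plan is narrower: the method is unnamed, and the figure does not carry over to the interval that will be used.

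A second objection is that 99.3% itself rests on the score statistic, which the SAP shows only in code that may be used. That is correct. It is why the figure is conditional here, and why naming the statistic matters more than changing the percentage. A third is that 99.3% assumes no Per Protocol losses. That is also correct, so any restated figure should carry the condition.

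A reader might also take the two mean-deviation figures as a contradiction. They are not: greater than 85% is a lower bound that >99.9% satisfies. Its agreement with SD 5.6 and 142 per arm suggests text carried over from the earlier design, but no document states that origin.

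Finally, one might infer that the reduction to 187 leaves the trial underpowered. With the score statistic and the 1% assumption, it does not. Protocol 9.1 also powers the study on mean deviation, not on the primary endpoint.

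**Conclusion.** The point holds as a minor correction. The >99.9% in Protocol 9.1 and SAP 2.3 is reproducible by approximation but is not delivered by the planned unconditional exact interval. With the score statistic, a 1% rate in each arm and about 93 evaluable per arm, power is about 99.3%, and it is lower if the Per Protocol set shrinks enough (97.5% at 80 per arm). The sample size stays adequate and the decision rule is unchanged.

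The part with real consequences is the unnamed statistic. The SAP text outside the code allows an ordering under which power would be about 0.1%. The code points to the score statistic, so nothing shows that the other ordering is intended; the text should simply rule it out. The mean-deviation sentence is editorial: true as a lower bound, but not the value for its stated inputs.

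**What to change.** 1. In Protocol 9.1 and SAP 2.3 (primary sentence and Table 2), restate the power as >99% (unconditional exact CI, score statistic, 1% per arm, about 93 evaluable per arm, no Per Protocol exclusions). The conditions belong in the statement, since 90 per arm already gives 98.96%.
2. In the SAP 8.1 and 8.2.1 text, name the score statistic for the unconditional exact interval, so that it applies whether StatXact or the SAS code is used. Do this before unblinding.
3. Editorial: in the mean-deviation sentence of both documents, replace greater than 85% with >99.9%, to match Table 1.
4. Optional tidying: bring the Summary's >90% into line with the restated figure, and update nper=142 in the example code, which is labelled hypothetical, to the current arm sizes.

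The cost is a few sentences, one Table 2 cell in each document and, if taken up, the code arguments. The stated primary power becomes slightly less favourable. No patients are added and the margin and decision rule stay as they are.

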This is a Phase IV, multicenter, randomized placebo-controlled trial to further characterize visual fields in subjects with partial epilepsy dosed for 13 weeks, including a 1 week up titration and 1 week down titration from the target dose of pregabalin 300 mg/day versus placebo. Comprehensive ophthalmologic testing will be done at pre-treatment baseline to exclude those with pre-existing eye disease.

Approximately 187 subjects will participate in the study. Subjects will be randomized 1:1 to pregabalin or placebo, with approximately 93 randomized to pregabalin and 93 to placebo.

Endpoints:

The primary endpoint is the proportion of subjects with a decrease in the threshold value from baseline to termination in five or more points (in either eye) at the $p < .05$ level repeated in the same five points on subsequent computerized automated perimetry testing (Humphrey 24-2 SITA standard).

Trial Treatments:

Subjects will receive oral pregabalin 75 mg twice daily (BID) (150 mg/day) or matching placebo for titration and taper. Subjects will receive oral pregabalin 150 mg BID (300 mg/day) or matching placebo for the treatment phase.

Statistical Methods:

The primary endpoint will be analyzed using a non-inferiority analysis. The difference in proportions between pregabalin and placebo in the per protocol population will be compared using a 2-sided 95% confidence interval (CI). Non-inferiority will be demonstrated if the upper CI bound is less than 0.10 (10%). The proposed sample size will have >90% power to detect non-inferiority on the primary endpoint, assuming a proportion of 1% for each group.

SCHEDULE OF ACTIVITIES

Protocol Activity	Screening	Baseline	Wk 0 Randomization	Wk 1	Wk 6	Wk 12 (Or ET)	Week 15 (Follow-Up)
Visit Number ⁿ	1	2	3 ^m	4	5	6	7
Informed Consent	X						
Inclusion/Exclusion Criteria	X	X	X				
Review/document contraception use	X						
History/Diagnosis/Demographics	X						
Physical Examination ^p	X					X	
Concomitant Medication	X	X	X	X	X	X	X
Body Weight	X	X		X	X	X	X
Vital Signs (Sitting BP/HR)	X	X		X	X	X	
ECG (Singlet)	X						
EEG	X ^a						
CT or MRI	X ^b						
Clinical	1) Hematology ^c	X				X	
Laboratory	2) Chemistry ^d	X				X	
	3) Urinalysis ^e	X				X	
Urine Pregnancy Test ^f	X					X	
Urine Drug Screen	X						
Ophthalmic Examination	1) External Eye Exam	X				X	X ^g
	2) ETDRS Acuity	X	X		X	X	X ^g
	3) Intraocular Pressure	X					
	4) Dilated Funduscopic	X					
	5) VFT (24-2 SITA)	X ^{h,i}	X ^{h,i}			X ^h	X ^h

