Formal visual field testing was conducted in over 2400 patients treated with pregabalin for neuropathic pain, chronic pain syndromes, intractable epilepsy, or generalized anxiety disorder in randomized controlled clinical trials of up to 3 months in duration and in over 3600 patients in open-label trials of up to 4 years in duration. Ophthalmologic assessments were included in the program due to concerns expressed at the time on emerging reports of visual field disturbances with the anticonvulsant vigabatrin, a gamma-aminobutyric acid (GABA)-transaminase inhibitor.³⁻¹¹ The mechanism of the visual field defects with vigabatrin is unknown but was considered as possibly related to its GABA mechanism. As a structural derivative of GABA, regulatory agencies considered similarity of pregabalin to vigabatrin as possible. Subsequently, it became clearer that the mechanism of action of pregabalin was not related to GABA-transaminase inhibition or to a GABA related mechanism. While the mechanism of action of pregabalin is not completely understood, results in animal models indicate that binding to the alpha-2-delta subunit of voltage-gated calcium channels may be involved in the activity of pregabalin.

In controlled pregabalin studies, a higher proportion of patients treated with pregabalin reported blurred vision (6%) than did patients treated with placebo (2%), which resolved in the majority of patients during treatment. In patients assessed with prospectively planned ophthalmologic testing, visual acuity was reduced in 7% of patients treated with pregabalin, and 5% of placebo-treated patients. Visual field changes were detected in 13% of pregabalin-treated, and 12% of placebo-treated patients. Funduscopy changes were observed in 2% of pregabalin-treated and 2% of placebo-treated patients.

This study is a Post-Authorization Safety Studies (PASS). It is being conducted as a commitment agreed upon with the United States Federal Drug Administration (FDA) regulatory agency.

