3. TRIAL DESIGN

This is a Phase IV, multicenter, double-blind, randomized, placebo-controlled trial to measure visual field sensitivity in subjects with partial epilepsy dosed with pregabalin or placebo. Pregabalin will be dosed at 300 mg/day for 11 weeks after one-week initiation with 150 mg/day, followed by one-week tapering of 150 mg/day. Total treatment period will be 13 weeks. Comprehensive ophthalmologic testing will be done at pre-treatment baseline to exclude subjects with pre-existing eye disease.

A central reader will assure the quality of all visual field test results with pre-specified criteria. Any field failing this quality assurance criteria either due to poor subject compliance or due to failure to follow testing procedures will be repeated as soon as possible within 2 weeks following notification from the central reader. Prior to randomization subjects must

meet the pre-specified quality assurance criteria. Subjects failing to meet this criteria at Baseline either due to poor subject compliance or due to failure to follow testing procedures can be re-screened one additional time after 3 months and will keep their previously assigned ID number. Rescreening may also be allowed for subjects with non-lesional epilepsy who may have been screen failed for reasons other than those specified above, if correctable.

Approximately 187 subjects will participate in the study. Subjects will be randomized 1:1 to pregabalin or placebo, with approximately 93 randomized to pregabalin and 93 to placebo.

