9.4. Safety Analysis

9.4.1. Analysis of Primary Endpoint

- **Definition:** The primary endpoint is the proportion of subjects with a decrease in the threshold value from baseline to termination in five or more points (in either eye) at the $p < .05$ level repeated in the same five points on subsequent computerized automated perimetry testing (Humphrey 24-2 SITA standard).
- **Baseline:** Baseline is determined from the last VFTs prior to receiving investigational product. A point will be considered abnormal at baseline only if it was abnormal (< 0.05) at both baseline tests.
- **Termination:** Termination is the VFT done at Week 12 (including a repeat test if applicable). For subjects who did not complete the study, the last available test(s) after Day 1 will be used. Data will not be imputed for subjects who do not have any VFTs after baseline; rather, such subjects will be treated as missing values.
- **Comparison:** The difference in proportions between pregabalin and placebo will be compared using a 2-sided 95% confidence interval (CI). Non-inferiority will be demonstrated if the upper CI bound is less than 0.10 (10%).
- **Populations:** The intent-to-treat (ITT) population is defined as all subjects randomized to treatment who received at least one dose of investigational product. The Per Protocol population is a subset of the ITT population, and excludes subjects who had a decrease in at least 5 points at termination but did not return for a repeat test. The Per Protocol population may also exclude subjects with major protocol violations; the list of subjects excluded will be determined prior to breaking the blind. The primary analysis will be performed on the Per Protocol population, the expectation is that the Per Protocol subset will be close in the number of subjects to the number of subjects randomized. A supplementary analysis of the primary parameter will be performed using the ITT population.

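### The stated >99.9% power for the primary endpoint is about 99.3% with the planned exact interval at the plan's own 1% rate, and that unsourced rate is shown without any sensitivity range

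*Protocol*

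**What the plan says.** Protocol section 3 sets the size: "Approximately 187 subjects will participate in the study". It adds the split: "Subjects will be randomized 1:1 to pregabalin or placebo, with approximately 93 randomized to pregabalin and 93 to placebo".

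Protocol 9.1 and SAP 2.3 then give >99.9% power for the primary endpoint, "assuming a proportion of subjects meeting primary endpoint definition of 1% for both groups", with a margin of 10 percentage points on the upper bound of a 2-sided 95% confidence interval. Table 2 in each document has that one row and no other. The Protocol Summary (Statistical Methods) claims >90% for the same endpoint, "assuming a proportion of 1% for each group". No source for the 1% is given in any of these places.

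The mean deviation SD is treated differently. It was changed from 5.6 dB to 1.3 dB using the blinded dataset of 15 March 2019, and the protocol says this value "was used to re-estimate the sample size for the secondary endpoints".

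SAP 8.1 chooses unconditional exact methods for the primary interval because it expects small proportions. Its alternative SAS code asks for an exact score-based risk difference and a Newcombe interval. The worked example in that code has 4 deteriorations, all on pregabalin, with 142 subjects per arm.

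**The concern.** Two things do not fit together. First, the power in Table 2 should describe the analysis that will be run. Exact unconditional intervals are more conservative than the normal approximation when events are rare, and rare events are what this plan assumes. Second, the trial was resized on blinded data for a secondary endpoint, while the only sizing input of the primary endpoint remains a single figure without a source.

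Against a fixed margin on the risk difference, power depends strongly on the common event rate. A reader of Table 2 cannot see this. The trial is a regulatory safety commitment, so it matters that a failed non-inferiority test can be read correctly. At a few percent per arm, a drug with no effect on visual fields would have a noticeable chance of missing the margin.

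**Working it through.** **Inputs.** 187 subjects at 1:1, taken as 93/93 and as 94/93 or 93/94 (pregabalin/placebo) (Protocol section 3). Margin 0.10 and 2-sided 95% interval, equivalent to one-sided 0.025 (Protocol 9.4.1, SAP 4.2). Rate 1% in both arms (Protocol 9.1, SAP 2.3). Unconditional exact method (SAP 8.1), with the score statistic as ordering because the SAS code names it.

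**Step 1: reproduce the plan's figure.** With the normal approximation, power = Φ(0.10/SE − 1.96), where SE = √(2p(1−p)/93).

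- At p = 0.01, SE = √(0.0198/93) = 0.01459.
- 0.10/0.01459 − 1.96 = 6.85 − 1.96 = 4.89, so power exceeds 99.99%.

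The stated >99.9% therefore reproduces. A Wald interval with exact binomial enumeration also gives 99.97%.

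**Step 2: use the planned method.** For every pair of event counts, compute the score statistic for a difference of 0.10, and maximise the one-sided p-value over the unknown placebo rate. Non-inferiority passes when that p-value is at most 0.025. Power is the sum of the joint binomial probabilities over the passing pairs. At 1% in both arms it is 99.3%. The Newcombe interval in the SAP code also gives 99.3%.

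**Step 3: the decision rule in counts.** At 93 per arm with no placebo events:

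- 3 pregabalin events pass (p = 0.015).
- 4 pregabalin events fail (p = 0.038). The Newcombe upper bound for 4 v 0 is 10.5%, also above the margin.

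At 142 per arm, up to 7 pregabalin events pass against none on placebo, and the Newcombe upper bound for 4 v 0 is 7.0%. The SAP's example split passes at the sample size in its code and fails at the current one.

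**Step 4: vary the rate.**

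| True rate | Exact, 93/93 | Exact, 94/93 | Exact, 93/94 | Normal approx., 93/93 | Exact, 142/142 |
|---|---|---|---|---|---|
| 1% both | 99.3% | 99.3% | 99.3% | >99.99% | 99.99% |
| 2% both | 95.8% | 95.6% | 95.8% | 99.8% | 99.7% |
| 3% both | 90.2% | 89.9% | 89.7% | 97.9% | 98.7% |
| 5% both | 78.5% | 77.8% | 76.2% | 87.9% | 93.9% |
| 12% both (extreme case) | 51.6% | 50.2% | 50.2% | 55.5% | 71.2% |
| 13% v 12% (extreme case) | 42.4% | 40.9% | 40.9% | 45.9% | 60.5% |

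At 93/93, power drops below 90% at a common rate of about 3.0% (exact) or 4.6% (normal), and below 80% at about 4.7% or 6.3%.

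**The case against.** The best defence is that the documents state power conditionally on 1%, that the normal approximation confirms the figure, and that 99.3% against >99.9% is a small gap. All of that is true. The plan is also consistent in expecting rare events: SAP 8.1 says so, and its example amounts to 4/284 = 1.4%. That example is labelled hypothetical, however, so it is not a source for the 1%. The remaining gap lies between the stated power and the planned analysis.

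The size of the sensitivity depends on the method. At 3% it is 90% exact against 98% normal. The reduction from 142 to 93 per arm costs 98.7 − 90.2 = 8.5 points at 3% by the exact method, but only 99.9 − 97.9 = 2.0 by the normal approximation. The fall in power should therefore always be quoted with its method.

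A reader might go further and infer that true power is only about 41-52%, because the Protocol Background reports "Visual field changes were detected in 13% of pregabalin-treated, and 12% of placebo-treated patients". The documents do not support that. The Background figure is undefined, is not said to be confirmed on repeat, and comes from earlier trials across several indications. This endpoint needs at least 5 newly abnormal points and at least 5 of the same points abnormal again in the same eye (SAP 6.2, Appendix A.1.2), in subjects screened for eye disease and test reliability. Its rate could well be much lower.

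A reader might also infer that the sponsor never compared the 1% with blinded data. The documents are silent on this; they report no such comparison, which is not the same thing.

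**Conclusion.** The concern stands as a correction to a stated power and a missing justification. At 187 subjects, 1% per arm and a 10% margin, the planned exact interval gives about 99.3%, not >99.9%. The Summary's >90% is true at 1% by every method tried, and stays true by the exact method up to a rate of about 3%.

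The larger practical point is the rate. It has no source, and exact power is about 96% at 2%, 90% at 3% and 76-78% at 5%.

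These figures assume equal true rates in the two arms, score-statistic ordering for the exact interval, and all randomized subjects in the Per Protocol set, which the plan expects to be nearly complete. With 88 or 84 per arm, exact power at 1% would be 99.0% or 97.3%. The range of 1% to 5% is an assumption, since neither document reports a rate for this endpoint.

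**What to change.** In Protocol 9.1 and SAP 2.3, both the text and Table 2:

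- Replace >99.9% with the figure from the planned exact method, about 99.3% at 1%, and name the method.
- Base the rate on the pooled blinded proportion of subjects meeting the SAP Appendix A.1.2 definition in the 15 March 2019 dataset, and state power at that rate.
- Show exact power at 1%, 2%, 3% and 5%. If 12-13% is shown at all, label it an extreme case (about 41-52%) and say that it comes from a different, undefined finding.
- Keep the Summary's >90% if the pooled blinded rate is below about 3%, and align its wording with Table 2.

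The sample size and margin stay as they are, and nothing needs unblinding. The cost is one pooled count from a dataset already prepared, plus table rows and wording. The downside is a slightly less favourable stated power.
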